The current project seeks to evaluate ways to improve outcomes for low-education, uninsured or Medicaid-eligible smokers who do not quit with standard quit line treatment. The current proposal will use an efficient factorial design to evaluate four evidence-based strategies to improve follow-up WTQL care offered to socioeconomically disadvantaged callers who report smoking four months following initial WTQL treatment comprising a single counseling call and 2-week supply of a single nicotine replacement therapy. These strategies include: increasing the intensity of nicotine replacement medication (among those medically cleared to use such medications), increasing the intensity of WTQL counseling, helping callers enroll in an evidence-based smoking cessation texting support program (SmokefreeTXT), and offering moderate financial incentives for engagement in counseling and SmokefreeTXT. This evaluation will identify which program enhancements, and which combination of program enhancements, improve abstinence rates in this high-priority and high-risk segment of the population served by the WTQL.

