### **II. GOALS/AIMS**

The overarching aim of the proposal is to evaluate ways to enhance quit line treatment for low-income smokers in terms of abstinence, costs, and reach. The specific aims of the project are listed below.

1. To assess the main and interactive effects of the four experimental factors (see below) on biochemically confirmed, 7-day point-prevalence abstinence at 6-month follow-up among low-education, uninsured, or Medicaid-eligible smokers who relapse following a standard WTQL intervention. Secondary abstinence outcomes are self-reported point-prevalence abstinence 12-weeks post-quit and continuous abstinence between months 1 and 6 post-quit.

Factors	Levels
1. Quit line counseling intensity	1. 1 vs. 4 proactive counseling calls
2. Nicotine replacement therapy (NRT) intensity	2. Patch (2 wks) vs. Patch+ Lozenge (4 wks)
3. SmokefreeTXT text messages	3. Proactive enrollment vs. none
4. Financial incentives for treatment engagement	4. \$30-\$150 vs. none
2. To evaluate the cost-effectiveness of each intervention component overall and in the context of the other components (i.e., additive and interactive effects and their impact on cost-effectiveness). The aim is to develop data to inform future quit line care planning and policy.	
3. To identify demographic and smoking history moderators of treatment engagement and response and mediators of intervention effects (e.g., treatment engagement) on 6-month abstinence. This aim will identify sub-populations that may not benefit equally from enhanced WTQL services and will suggest ways to refine the treatments to enhance their efficacy.	

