### **D. Randomization**

Randomization will occur immediately after baseline data are collected after oral consent is obtained and will be conducted by WTQL staff using randomization tables developed at UW-CTRI. Randomization will be blocked by ethnicity and race to ensure an even distribution of participants of these factors that may relate to intervention success. Enrollees will be randomized to one of 16 conditions, as shown above. No placebo will be used in this real-world trial. Every enrollee will receive no less than the current standard in WTQL care, a single counseling session, a 2-week supply of a single nicotine replacement therapy (if medically eligible for nicotine medication), and unlimited access to a WTQL Quit Coach by request.

Following randomization, WTQL staffers will describe the randomized interventions in accessible language. This will include description of the counseling offered; description of the medications to be mailed to the participant; information about SmokefreeTXT; and a description of relevant incentives and their contingencies (i.e., \$30 for each counseling call lasting, \$30 for staying in SmokefreeTXT for the full 6 weeks post-quit).

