## F. Study treatments and experimental conditions

All study participants will be offered a second round of standard evidence-based WTQL treatment comprising a single counseling call and, if medically eligible, a 2-week supply of a single nicotine replacement therapy (this will be the nicotine patch for everyone to reduce heterogeneity in regimens and because data suggest that adherence to nicotine patch therapy is superior to that of nicotine gum or lozenge). Everyone will receive care that meets or exceeds the current standard of care for WTQL services to Wisconsin residents. Participants will be randomized to additional interventions to supplement this base treatment. None of the interventions to be added as supplements to standard WTQL is experimental, as all have data to support their efficacy. In fact, a multi-call protocol used to be the standard of care for the WTQL prior to budget cuts. Adding a fast-acting nicotine replacement therapy (NRT) to nicotine patch (called combination NRT) is an accepted treatment supported by meta-analyses and approved by FDA. Meta-analyses also support the effectiveness of text messaging support programs for smoking cessation like SmokefreeTXT. Growing evidence, including two previous program evaluation projects for Medicaid-eligible Wisconsin smokers coordinated by UW-CTRI, supports the efficacy of incentives as a driver of treatment engagement and, thereby, of long-term abstinence rates. The

Cell	WTQL	NRT (if eligible)	Texts	Incentives
1.	1 call	2 wk Patch	SmokefreeTXT	Yes, up to \$60
2.	1 call	2 wk Patch	SmokefreeTXT	No
3.	1 call	2 wk Patch	None	Yes, up to \$30
4.	1 call	2 wk Patch	None	No
5.	1 call	4 wk Patch+Lozenge	SmokefreeTXT	Yes, up to \$60
6.	1 call	4 wk Patch+Lozenge	SmokefreeTXT	No
7.	1 call	4 wk Patch+Lozenge	None	Yes, up to \$30
8.	1 call	4 wk Patch+Lozenge	None	No
9.	4 calls	2 wk Patch	SmokefreeTXT	Yes, up to \$150
10.	4 calls	2 wk Patch	SmokefreeTXT	No
11.	4 calls	2 wk Patch	None	Yes, up to \$120
12.	4 calls	2 wk Patch	None	No
13.	4 calls	4 wk Patch+Lozenge	SmokefreeTXT	Yes, up to \$150
14.	4 calls	4 wk Patch+Lozenge	SmokefreeTXT	No
15.	4 calls	4 wk Patch+Lozenge	None	Yes, up to \$120
16.	4 calls	4 wk Patch+Lozenge	None	No

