## Analysis Plan

To assess Aim 1, we will test the main and interactive effects of counseling intensity, NRT intensity, SmokefreeTXT, and engagement incentives on biochemically confirmed, 7-day point-prevalence abstinence at 6-month follow-up. Secondary abstinence outcomes are self-reported point-prevalence abstinence 12-weeks post-quit and continuous abstinence between months 1 and 6 post-quit.

*Measures, Populations and Analysis:*

Data for the primary, abstinence-focused analyses will include randomized levels of the treatment factors and their interactions as independent variables, binary abstinence outcomes based on self-reported abstinence (at 12-week follow-up) and biochemical verified abstinence (at 26-week follow-up only) as the dependent variables, and covariates such as demographics and smoking history collected at registration or enrollment.

The population will be the eligible, consented, enrolled subjects who were randomized to treatment. Participants who were randomized but did not complete the study will be included in analyses (unless they requested that their data not be used upon withdrawal from the study). Analyses will occur in the full intent-to-treat sample.

Logistic regression analyses will be used to estimate intervention main and interactive effects on binary abstinence outcomes. Both unadjusted models and models adjusted for covariates will be run. Separate models will be run for different outcomes (e.g., biochemically confirmed abstinence at 26-weeks post-quit, self-reported abstinence at 12 weeks post-quit, continuous abstinence between 4 and 26-weeks post-quit) under different assumptions regarding missing abstinence data (e.g., assuming all missing are smoking, assuming 80% of missing are smoking, using multiple imputation).

*Data Sources and Collection:* The primary outcome data will be collected by UW-CTRI via telephone follow-up interview and in-person, mailed, or emailed validation of abstinence via CO breath testing and/or urinary or salivary cotinine testing. Covariates will be assessed by WTQL staffers at registration or enrollment and transferred securely to UW-CTRI for analysis.

To assess Aim 2, we will evaluate the costs and cost-effectiveness of each intervention component overall and in the context of the other components (i.e., additive and interactive effects and their impact on cost-effectiveness).

*Measures, Populations and Analysis:*

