**Describe how ALL the risks of the study will be minimized.**

To protect against breach of confidentiality or violations of privacy, we will ensure that data are stored on secure, encrypted servers at all participating sites, and that transfer of data between sites is conducted via HIPAA-compliant means. A unique study ID will be used to store all data on individual participants and information linking that study ID to participant identifying information will be maintained by the data manager. Data being used for analysis will be identified with the study ID only. Participant contact information will only be available to study staff having direct contact with participants. Data will be stripped of direct identifiers (limited datasets) or completely de-identified prior to sharing with others outside the IRB-approved research team.

To protect against adverse reactions to over-the-counter nicotine medication, the WTQL will screen participants for eligibility using their standard, physician-reviewed protocol over the phone and participants will receive simple, clear instructions in their proper use in the mailing sent post-enrollment. These forms will advise participants of common side effects and will describe ways to prevent or address these (i.e., putting a new patch on a different part of the body each day, taking the patch off at night if sleep disturbance is too bothersome). These medication instruction forms and all written study materials will be written at no higher than a sixth-grade reading level. In addition, people who report recent cardiac-related surgeries or hospitalizations, and those with allergies or past negative reactions to nicotine replacement, will be screened out of medication eligibility at enrollment to further reduce risks of nicotine administration. All Quit Coaches receive training on smoking cessation pharmacotherapy and assess medical conditions that may preclude or complicate NRT use at registration. In addition, Quit Coaches have access to Optum physicians who can address questions or concerns about pharmacotherapies. Optum will conduct routine monitoring for adverse or unanticipated events according to their standing protocols.

Participants will be alerted to possible withdrawal effects at enrollment, will be offered over-the-counter medication to manage these symptoms (if medically eligible), and will be advised that these symptoms are typically mild and temporary.

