To facilitate participant safety, study participants must meet study inclusion and exclusion criteria. Once enrolled, WTQL protocols will assess NRT eligibility and the presence of AEs and SAEs during treatment. Should either excessive risk to study participants and/or convincing evidence of lack of measurable benefit to study participants be determined, the study will be stopped and all participants notified in a manner appropriate to the nature of the risk and/or lack of benefit. When taking that step, the investigators will consult with the IRB and NCI.

Plans for assuring compliance with requirements regarding the reporting of adverse events. This DSMP requires that investigators notify NIH and the University of Wisconsin IRB in a timely manner (consistent with IRB and NIH policies) of the occurrence of any SAE or any AE which is severe, unexpected, and possibly related to study medication or protocol. Because this study involves pharmaceutical agents, if an unexpected SAE might be related to study drug use, both the Food and Drug Administration (FDA) and the manufacturer will also be notified within 5 days of investigators becoming aware of the event. Examples of unexpected SAEs would be untoward medical or intervention occurrences that result in death, are life-threatening, require hospitalization or prolonging of existing hospitalization, create persistent or significant disability/incapacity, or involve congenital abnormality/birth defects. Unanticipated AEs include less serious problems that merit reporting to the DSMC because they are severe, unexpected, and possibly related to study participation. Any SAE will be queried and reported even if it appears that the serious adverse event is unrelated to study participation. Because the interventions will be delivered by our WTQL partner, Optum, staff there will be responsible for assessing and managing any adverse events related to study medication in accordance with their existing protocols for monitoring NRT medication side effects or unanticipated health events during counseling calls. The study team will review Optum reports of unanticipated health events no less than bi-weekly, and Optum will notify the PIs of any severe, unanticipated, and possibly study-related adverse events in a timely manner so that NIH, FDA, and the IRB may be notified, as needed.

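### People not medically eligible for NRT are randomized on the NRT factor but have no NRT contrast; no analysis in eligible participants is pre-specified, and the plan does not say that eligibility is recorded before assignment is revealed

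*Combined protocol and SAP*

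**What the plan says.** **Who the NRT strategy is for.** The Significance section describes it as "increasing the intensity of nicotine replacement medication (among those medically cleared to use such medications"). Aim 1, under Goals/Aims, names the wider population of disadvantaged smokers who relapse after standard treatment, with no restriction to people cleared for NRT.

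**Who receives it.** Section D promises every enrollee at least "a 2-week supply of a single nicotine replacement therapy (if medically eligible for nicotine medication"). Section F repeats the condition for the base treatment ("if medically eligible, a 2-week supply of a single nicotine replacement therapy"), and the NRT column of its 16-cell table carries the condition for every cell. The Treatment procedures description applies it to the enhanced level too.

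**Who is excluded.** The only exclusion in Section A concerns pregnancy, breastfeeding or planned pregnancy. Under the risk-minimization heading of Section H, people with recent cardiac surgery or hospitalization, an allergy, or a past bad reaction to NRT "will be screened out of medication eligibility at enrollment". They lose the medication, not their place in the study. The same heading also says that NRT goes to all participants, and then limits it to those medically eligible.

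**Analysis.** For Aim 1: "Analyses will occur in the full intent-to-treat sample". The Aim 3 text allows moderator and subgroup analyses and lists health status, but does not name NRT eligibility. Randomization is blocked by race and ethnicity only (Section D).

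**Timing.** Section D places randomization directly after consent and baseline data. Section H puts the eligibility check at enrollment and says that coaches assess relevant conditions at registration. The Data Safety and Monitoring Plan says "Once enrolled, WTQL protocols will assess NRT eligibility".

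**The concern.** An ineligible participant gets the same NRT care, namely none, at either NRT level. Such people cannot contribute an NRT effect, so they shrink the observed difference and add variance to it. NRT is the only one of the four factors with an explicit medical gate. The trial is meant to show which enhancements work, so dilution could make NRT look weaker than its effect in those who can use it. The same abstinence data feed the cost-per-quit estimates of Aim 2.

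The natural complement is an analysis in eligible participants. It remains a randomized comparison only if eligibility was fixed independently of the assigned level. Quit line staff screen, randomize and deliver treatment, and only the follow-up staff are stated to be blind (Section G). If the order of the check and the assignment is undocumented, a reader cannot confirm that the eligible subset is a baseline subset. An eligible-only analysis chosen after the results are known would also look post hoc.

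**Working it through.** The documents give a sample size but no alpha, power, abstinence rates, effect size or ineligible share, so there is no stated power figure to reproduce. What follows is an illustration.

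**Input from the documents.** 1,408 to 1,600 randomized (Section A). Half go to each NRT level: 1,408/2 = 704, or 1,600/2 = 800.

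**Assumptions.** Among eligible participants, abstinence is p1 = 10% at the lower level and 15% at the enhanced level. Ineligible participants quit at 10% whatever their level. Two-sided alpha is 5%. The ineligible share f runs from 2% to 30%.

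**Formulas.**
- Full-sample difference = 5 points × (1 − f), with n per level.
- Eligible-only difference = 5 points, with n × (1 − f) per level.
- Power = Φ[(d − 1.96·SE0)/SE1], where SE0 = √(2·p̄(1 − p̄)/n) and SE1 = √([p1(1 − p1) + p2(1 − p2)]/n).

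**Example, f = 20%, 704 per level.**
- Full sample: 10% vs 14%, p̄ = 0.12. SE0 = √(2 × 0.1056/704) = 0.01732; SE1 = √(0.2104/704) = 0.01729. Power = Φ[(0.04 − 0.03395)/0.01729] = Φ(0.350) = 63.7%.
- Eligible only: 704 × 0.8 = 563 per level, 10% vs 15%, p̄ = 0.125. SE0 = √(2 × 0.109375/563) = 0.01971; SE1 = √(0.2175/563) = 0.01966. Power = Φ[(0.05 − 0.03863)/0.01966] = Φ(0.578) = 71.8%.

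**Results.** With nobody ineligible, power is 81.0% at 704 per level.

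| Ineligible share | Full-sample difference (points) | Full sample, 704 | Eligible only, 704 | Full sample, 800 | Eligible only, 800 |
|---|---|---|---|---|---|
| 2% | 4.90 | 79.6% | 80.2% | 84.4% | 85.0% |
| 5% | 4.75 | 77.3% | 79.0% | 82.3% | 83.9% |
| 10% | 4.50 | 73.1% | 76.8% | 78.4% | 81.9% |
| 20% | 4.00 | 63.7% | 71.8% | 69.2% | 77.2% |
| 30% | 3.50 | 53.2% | 66.1% | 58.5% | 71.6% |

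The eligible-only analysis recovers only part of the lost power, because it uses fewer people.

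**If eligibility were judged after assignment.** Suppose NRT has no effect, abstinence is 15%, and at one level an extra share g of participants with quit probability q is screened out. The eligible-only comparison then shifts by (0.15 − g·q)/(1 − g) − 0.15. With g = 2% and q = 5% this is 0.149/0.98 − 0.15 = 0.2 points. With g = 5% and q = 0 it is 0.15/0.95 − 0.15 = 0.8 points. The values of g and q are hypothetical.

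**The case against.** Four points can be made for the plan.

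1. **The full-sample estimate is a policy quantity.** A quit line offers NRT to callers some of whom cannot use it, Aim 2 is meant to inform quit line planning, and Aim 1 names no eligible-only population. A reader might infer that the intent-to-treat result is biased. The documents do not support that: it validly estimates the effect of the offer, and it is smaller only relative to the effect in cleared participants. The Significance wording may also simply say who is dispensed medication. This stands, and it is why the full-sample analysis should stay.

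2. **The timing can be read as consistent.** A reader might infer from the monitoring plan that eligibility is judged after assignment. In the Schedule of Study Activities, however, people are counted as enrolled at oral consent, and baseline data and then randomization follow. An enrolled participant may therefore still be unassigned, and the three descriptions may be successive checks. This stands too: assessment after assignment is possible but not shown. What remains is that no text says eligibility is recorded before assignment is revealed.

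3. **Subgroup analyses are already allowed.** The Aim 3 examples are not a closed list, and an eligible subgroup would fit. But NRT eligibility is not named, so the analysis is permitted rather than pre-specified.

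4. **The ineligible share may be small.** Pregnancy is already excluded, the named medication screen-outs are few, and standard treatment before enrollment includes a two-week NRT kit. Against this, the prerequisite in Section A is engagement in counseling, not receipt of NRT, and the full screening protocol is not in the documents. Small shares are plausible, and there the gain is slight: under 1 point of power at 2% and under 2 points at 5%.

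**Conclusion.** The point holds as a matter of estimand, power and pre-specification, not of validity. Ineligible participants are randomized on the NRT factor, have no NRT contrast, and are included in the only analysis specified for Aim 1. The full-sample NRT difference is therefore (1 − f) times the effect in eligible participants, given no effect in the ineligible.

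The size depends on a share that the documents do not give. Under the assumed 10% vs 15% and 704 per level, an eligible-only analysis adds little power at 2% to 5% ineligible, about 4 points at 10%, 8 at 20% and 13 at 30%. The timing text leaves open, but does not establish, assessment after assignment. The change is a cheap improvement rather than a correction of an invalid analysis.

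**What to change.** - Keep the full-sample intent-to-treat analysis for all four factors, and say that for NRT it estimates the effect of offering the enhanced level to all enrollees.
- Beside it, pre-specify the NRT main effect and its interactions in participants who are eligible for NRT by data recorded before assignment. With eligibility fixed in this way the comparison stays randomized, even though eligibility is not a blocking factor.
- Reconcile Section D, the risk-minimization text in Section H and the Data Safety and Monitoring Plan, so that they agree that eligibility is recorded before assignment is revealed. The two Section H statements on who is given NRT must also be reconciled with each other.
- Report the ineligible share by assigned NRT level. It shows the size of the dilution, and a marked imbalance would be a warning about timing.

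The cost is analysis-plan wording, confirmation that the screening result is saved before randomization, and one extra reported analysis on a somewhat smaller sample. No treatment and no sample size changes.
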